825 For each concomitant illness, date of onset, date of resolution or continuing, at a 826 minimum, should be recorded.

827

828

829 10. ADVERSE EVENTS:

830 **10.1 Definitions**

831 The FDA approved version of the Prescribing Information or update thereof will be used
832 for assessment of expectedness.

833 **10.1.1 Adverse Event (AE):**

834 An AE is any undesirable medical event occurring to a subject in a clinical trial, whether or
835 not related to the trial product(s). This includes events reported from the first trial related
836 activity after the subject has signed the informed consent and until post treatment follow-
837 up period as defined in the protocol. The following should not be recorded as AEs, if
838 recorded as medical history/concomitant illness on the CRF at screening:

- 839 • Pre-planned procedure, unless the condition for which the procedure was planned has
840 worsened from the first trial related activity after the subject has signed the informed
841 consent
- 842 • Pre-existing conditions found as a result of screening procedures

843 **Clinical Laboratory Adverse Event:**

844 A clinical laboratory AE is any clinical laboratory abnormality regarded as clinically
845 significant i.e. an abnormality that suggests a disease and/or organ toxicity and is of a
846 severity, which requires active management, (i.e. change of dose, discontinuation of trial
847 product, more frequent follow-up or diagnostic investigation).

849 **Serious Adverse Event (SAE):**

850 A serious AE is an experience that at any dose results in any of the following:

- 851 • Death
- 852 • A life-threatening* experience
- 853 • In-patient hospitalisation or prolongation of existing hospitalization
- 854 • A persistent or significant disability/incapacity
- 855 • A congenital anomaly/birth defect
- 856 • Important medical events that may not result in death, be life-threatening*, or require
857 hospitalisation may be considered an SAE when, based upon appropriate medical
858 judgement, they may jeopardise the subject and may require medical or surgical
859 intervention to prevent one of the outcomes listed in this definition
- 860 • Suspicion of transmission of infectious agents

861 *The term life-threatening in the definition of SAE refers to an event in which the subject was at risk of death
862 at the time of the event. It does not refer to an event which hypothetically might have caused death if it was
863 more severe.

865 **Serious Adverse Drug Reaction (SADR):**

866 An adverse drug reaction (ADR) is an adverse event (AE) for which a causal relationship
867 to the trial product is at least possible i.e. causal relationship is conceivable and cannot be
868 dismissed. Serious adverse reaction (SAR): Adverse event which fulfils both the criteria
869 for a Serious Adverse Event and the criteria for an Adverse Reaction.

871 **Suspected Unexpected Serious Adverse Reaction (SUSAR):**

873 An SAE which is unexpected and regarded as possibly or probably related to the
874 trial/study product by the investigator.

875

876 **Medical Events of Special Interest (MESI):** A MESI is (1) a medication error (e.g. 877
wrong drug administration or wrong route of administration) or (2) a suspected 878
transmission of an infectious agent via the product

879

880 **Non-Serious Adverse Event:**

881 A non-serious AE is any AE which does not fulfil the definition of an SAE.

882

883 **10.2 Severity Assessment Definitions:**

- 884 • Mild: Transient symptoms, no interference with the subject's daily activities
- 885 • Moderate: Marked symptoms, moderate interference with the subject's daily activities
- 886 • Severe: Considerable interference with the subject's daily activities, unacceptable

887

888 **10.3 Relationship to study medication Assessment Definitions:**

- 889 • Probable: Good reasons and sufficient documentation to assume a causal relationship
- 890 • Possible: A causal relationship is conceivable and cannot be dismissed
- 891 • Unlikely: The event is most likely related to an etiology other than the trial product

892

893 **10.4 Outcome Categories and Definitions:**

894 • Recovered: Fully recovered or by medical or surgical treatment the condition has 895
returned to the level observed at the first trial related activity after the subject signed the 896
informed consent

897 • Recovering: The condition is improving and the subject is expected to recover from the 898
event. This term should only be used when the subject has completed the trial

899 • Recovered with sequelae: As a result of the AE, the subject suffered persistent and 900
significant disability/incapacity (e.g. became blind, deaf, paralysed). Any AE recovered 901 with
sequelae should be rated as an SAE

902 • Not recovered

903 • Fatal

904 • Unknown

905

906 **10.5 Collection, Recording and Reporting of Adverse Events**

907 All events meeting the definition of an adverse event will be collected and reported from 908
the first study-related activity after the subject has signed the informed consent and until 909 the
end of the posttreatment follow-up period as stated in the protocol.

910

911 We intend to comply with all local legal, regulatory, and IRB requirements.

912

913 All AEs will be reported on the Adverse Events form that will be completed by the study
914 staff, who are masked as to study treatment assignment, at each regular follow-up visits.

915 This will ensure that AEs are ascertained in an unbiased manner using the same 916
standardized methodology for patients in both treatment arms. Forms will include 917
standardized questions relating to specific events of import in diabetic patients on either 918 of
the study treatment arms, as well as any significantly abnormal physical findings 919
identified on examination and any significantly abnormal laboratory results obtained on 920 the
patient between visits or at the time of the visit. AEs reported or ascertained between 921 clinic
visits will be captured and reported at the time of the next scheduled visit. Pre- 922 existing
conditions (that is, any condition that was known to be present prior to the 923 signing of
informed consent or was identified during the screening procedures) will not 924 be considered
or recorded as AEs unless the condition worsens in intensity or frequency 925 after the initiation
of study intervention. Likewise, continuing AEs will not be reported 926 as AEs at subsequent
visits unless they increase in severity or frequency between visits, 927 they result in criteria for
a SAE, and/or they resolve between visits. The investigators 928 will report all adverse events
including SAEs, SUSARs, serious adverse drug reactions 929 (SADRs) to the competent
authority and independent ethics committee/IRB based upon 930 federal regulations and
local/IRB policies. The investigators will also report all SAEs, 931 SUSARs, and SADRs to
Novo Nordisk at the same time such events are reported to 932 regulatory authorities or within
15 days from the investigators becoming aware of such 933 adverse events, whichever comes
first.

934

935 The investigators will collect the following information at minimum for each of these
936 events:

937 1. Study name
938 2. Patient identification (e.g. initials, sex, age)
939 3. Event (preferably a diagnosis)
940 4. Drug
941 5. Reporter identification (e.g. Name, or initials)

942 Also 6) Causality, and 7) Outcome

943

944 **10.6 Follow-up of Adverse Events**

945 During and following a subject's participation in a clinical trial, the investigators and
946 institution will provide adequate medical care to the study subject for any study-related
947 adverse events, including clinically significant laboratory values related to the study.
948 This medical care for study subjects will be provided regardless of their insurance status.
949

950 All adverse events classified as serious or severe or possibly/probably related to the trial 951
product must be followed until the subject has recovered and all queries have been 952
resolved. For cases of chronic conditions follow-up until the outcome category is 953
“recovered” is not required, as these cases can be closed with an outcome of “recovering” 954 or
“not recovered”.

955

956 All other adverse events must be followed until the outcome of the event is “recovering”
957 (for chronic conditions), or “recovered” or until the end of the post-treatment follow-up

958 stated in the protocol, whichever comes first, and until all queries related to these AEs have
959 been resolved.

960

961 **10.7 Pregnancy**

962 Study subjects will be instructed to notify the investigators immediately if they become
963 pregnant.

964

965 The investigators will report to Novo Nordisk any pregnancy occurring during the trial
966 period. Reporting of pregnancy by investigators will occur within the same timelines
967 described above for reporting of Adverse Events.

968

969 Pregnancy complications should be recorded as adverse event(s). If the infant has a
970 congenital anomaly/birth defect this must be reported and followed up as a serious adverse
971 event.

972

973 **10.8 Precautions/Over-dosage**

974

975 All patients enrolled in the study will have access to and be instructed to wear a CGM from
976 day 0 until the completion of study intervention. Patients may continue to wear the CGM
977 as part of the standard of care for their diabetes beyond the study period. Use of a CGM
978 has been shown to be effective in preventing hypoglycemia, which is a possible
979 complication related to overdose of insulin, as well as morbidities and mortality related to
980 hypoglycaemia (11). Clinician investigators and/or research staff will also provide patients
981 with instructions on prompt recognition and proper treatment of hypoglycemia and
982 prescribe patients with glucagon kit to be used for treatment of hypoglycemia as needed.
983 Patients will have access to medical providers at the DCC by phone or e-care
984 communication if additional guidance is needed in the event of overdose by the study drug
985 during the study.

986

987

11. LIABILITY AND SUBJECT INSURANCE:

988

989 During and following a subject's participation in the clinical trial, the investigators and
990 their institution will provide adequate medical care to the study subject for any study-
991 related adverse events, including clinically significant laboratory values related to the
992 study. This medical care for study subjects will be provided regardless of their insurance
993 status.

994

995 The investigators will be responsible for the conduct of the study and agree to defend,
996 indemnify, and hold harmless Novo Nordisk, any of its parent companies, affiliates, or
997 subsidiaries, and their respective officers, directors, employees, agents, representatives,
998 distributors, salespersons, customers, licensees, and end-users from and against any claim,
999 suit, demand, loss, damage, expense or liability imposed by any third party arising from or
1000 related to: (a) any breach of Novo Nordisk-investigators' obligations or representations; or
1001 (b) Novo Nordisk-investigators' negligent or grossly negligent use or willful misuse of the
study drug, the results, or services derived therefrom. This

GLIDE Study

1002 indemnification shall not apply in the event and to the extent that a court of competent
1003 jurisdiction or a duly appointed arbiter determines that such losses or liability arose as a
1004 result of Novo Nordisk's gross negligence, intentional misconduct, or material breach of
1005 its responsibilities.

1006

1007

1008 12. EVALUABILITY OF SUBJECTS:

1009 For all analyses, patients not meeting the compliance criteria of the study listed under
1010 Section 3.13 will not be included in the analyses. Clinician investigators will determine
1011 patients' compliance with study drug based on patient's recorded log and patients' time
1012 spent wearing CGM after CGM data has been downloaded at the follow-up visit. We will
1013 include data from all randomized participants in our data analysis. The subjects or
1014 observations to be excluded, and the reasons for their exclusion will be documented and
1015 signed by the clinician investigators or staff prior to database release. The documentation
1016 will be stored together with the remaining trial documentation.

1017

1018 **PK and/or PD Modelling**

1019 PK and PD modelling is not planned for this study.

1020

1021

1022 13. PREMATURE TERMINATION OF STUDY:

1023 All patients participating in the study will have already been taking insulin glargine prior
1024 to their enrolment in the study. Therefore, we do not anticipate patients developing any
1025 unforeseen adverse effect associated with the administration of insulin glargine. Similarly,
1026 we do not anticipate patients developing any unforeseen adverse effect associated with the
1027 administration of the placebo (normal saline).

1028

1029 IDeg will be discontinued if a patient:

- 1030 • Experiences an SAE related to IDeg (with the exception of hypo- or
1031 hyperglycemia) or an intolerable AE, such as a persistent allergy or rash.
- 1032 • Becomes pregnant or breastfeeding
- 1033 • Withdraws consent for participation in the study

1034

1035

1036

1037

1038

1039

1040

1041

1042

1043 Date and reason for drug discontinuation will be recorded on the relevant Case Report
1044 Form. Refer to Section 3.7 for Withdrawal Criteria. All study discontinuations decided by
1045 the clinician investigators will be reviewed by University of Washington's IRB. Patients
1046 discontinued from the study will be placed back on their original home insulin regimen and
1047 asked to follow up with their outpatient endocrinologists within 2-12 weeks, or at an
1048 interval deemed appropriate by their outpatient endocrinologists. Major attempts will be
1049 made to schedule an end-of-study follow-up phone call for all patients who are lost to
1050 follow-up during the course of the study.

1051

1052

1053

1054

1055

1056

1057 Patients who discontinue study drug or withdraw consent from the study prior to
1058 completion of data collection will not be replaced.

1047 14. PUBLICATION PLAN:

1048 Data and results generated from the study will be published or publicly presented at
1049 national and/or regional meetings in the form of abstracts, posters, and/or oral
1050 presentations. Clinician investigators will make good faith effort to publish data and results
1051 of this study in a peer reviewed scientific journal. The clinician investigators intend to
1052 register the study with clinicaltrials.gov.

1053

1054

1055

1056

1057 15. REFERENCES:

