194 i. Patients transitioning from once daily insulin glargine to once daily IDeg with
195 a bridging dose of insulin glargine.
196 ii. Patients transitioning from twice daily insulin glargine to once daily IDeg
197 with a bridging dose of insulin glargine.

198 **2. Direct-Conversion Groups:**

199 i. Patients transitioning from once daily insulin glargine to once daily IDeg
200 without a bridging dose of insulin glargine (but with a bridging dose of
201 placebo solution to preserve blinding).
202 ii. Patients transitioning from twice daily insulin glargine to once daily IDeg
203 without a bridging dose of insulin glargine (but with a bridging dose of
204 placebo solution to preserve blinding).

205
206 All patients will be instructed to use their own prescription insulin medications till before
207 the 1st dose of IDeg. On the night they have to transition to IDeg, they will start using
208 study drugs for their basal insulin (see section 3.10.4). Starting with the 1st dose of IDeg,
209 their basal insulin will be from study drug only, till visit #3 (see section 3.10.6), at which
210 time, they will resume their original insulin prescriptions. They will remain on their own
211 prescription short-acting insulin throughout the study. On the night of the transition, all
212 patients will be instructed to take their 1st dose of IDeg and along with this, they will take
213 a second injection from a pre-filled syringe of a pre-specified dose of insulin glargine or
214 matched placebo (normal saline), that participants will collect from Investigational Drug
215 Services Pharmacy (IDS) on the same day. The dose will be calculated ahead of time by
216 study staff on visit 2 (see under section 3.10.2.1). Neither the patients, nor the research
217 staff will be aware of their randomization, which will be done by IDS. Patients will act as
218 their own controls, as we will collect glycemic data from 48 hours prior to the first dose
219 of IDeg, which will be compared to the data seen in the 48 hours after the first dose of
220 IDeg. During this observation period of the 48 hours before and after the first dose of
221 IDeg, no adjustments will be made to the calculated and recommended doses of insulin
222 glargine or IDeg. Patients will be followed for up to 1 week after the first dose of IDeg.
223

224 **3.3 Rationale for study Design**

225 Though IDeg is being increasingly used in clinical practice, there are no guidelines on

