473 *their blood glucose is >250, both around meals and otherwise.* While we understand that
474 subjects might be reluctant to allow their blood glucose to run in the 180-250 range
475 without correction, we feel this is a necessary part of our study protocol. The main reason
476 for this is that our primary study end point is time in range (TIR). If the change from
477 insulin glargine to IDeg results in more time in the 180-250 range in patients not
478 receiving the bridging dose of glargine, patients are likely to correct this aggressively
479 with the use of correctional insulin. This would dilute any measurable differences in our
480 primary end point (TIR). It would only potentially show differences in the secondary end
481 points of dose and number of correctional insulin used. However, by telling them to avoid
482 bolusing till glucose rises above 250, we will be able to discern any differences in TIR
483 that might arise from the change of basal insulin, while at the same time, not being unsafe
484 for the patients over a 96 hour period of time.

485

486 3.10.3 Telephone Encounters #1:

487 This will be on day 1 (i.e. the day after the study CGM is inserted). We will ensure that
488 the study CGM is working and the subject does not have any questions or concerns.
489 Study staff will also assist the subject with any troubleshooting, if necessary. Subjects
490 will be instructed to upload their CGM data on day 3, for research staff to review it.
491 Subjects will be instructed not to alter their insulin glargine dose for the following 48
492 hours, till the night of day 3, when they transition to IDeg. We will inquire about any
493 adverse events and change to concomitant medications and document doses of insulin
494 being administered by patient.
495

496 3.10.4 Telephone Encounter #2:

497 Research staff will review patient's CGM data upload on day 3. We will inquire about
498 adverse events, any change to concomitant medications and also document doses of
499 insulin being administered.
500 If there is \geq 38 hours of usable CGM data, then they will be instructed to proceed with
501 their first dose of IDeg that night, as scheduled. In order to obtain the bridging dose of
502 insulin glargine or matched placebo, subjects will be instructed to proceed to IDS at the
503 University of Washington to collect their study drug the same day.
504 If there is $<$ 38 hours of usable CGM data, then subjects will be instructed to wear their

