606 Compliance will be defined by the following (all 3 need to be met to be considered 607
607 compliant), assessed during the 48 hours prior to and after the first dose of IDeg:
611
612

- 608 • No missed doses of basal insulin
- 609 • No missed doses of nutritional insulin with meals
- 610 • Wearing the study CGM for >19 hours a day

613 4. STATISTICAL CONSIDERATIONS:

614 The primary objective of this pilot study is to calculate the change in percent time that 615 BG is “in range” (TIR defined as 70-180 mg/dL) in the 48 hours before the first IDeg 616 dose vs. the 48 hours after the first dose, and to compare the mean of this change between 617 patients who are randomized to receive bridging glargine and those who are randomized 618 to not receive bridging glargine. Randomization will be stratified by glargine use (once 619 vs. twice daily). For each patient, the TIR in the 48 hours before first IDeg use will be 620 calculated, as will the TIR in the 48 hours after first IDeg use. The difference of these 621 values will then be calculated, and the mean of the differences compared between the 622 randomized arms. Our primary hypothesis will assume that the “bridging effect” is 623 similar between patients who take glargine once daily and twice daily. However, we plan 624 an exploratory look at this assumption as a secondary objective.

625

626 If we assume the true change in TIR (before first dose of IDeg minus after first dose of 627 IDeg) to be 0% for the bridging group and 15% for the non-bridging group, and if we 628 assume a common standard deviation of 15% (meaning the distributions of change in TIR 629 are separated by 1 standard-deviation unit), then 20 patients in each group will provide 630 87% power to observe a statistically significant (at the two-sided level of .05) difference 631 in mean change of TIR.

632

633 As noted above, we’ll assess the magnitude of this difference as a function of once- vs. 634 twice-daily glargine use. With only 40 patients, it’s highly unlikely that a statistically 635 significant interaction will be observed, but if the directions of the difference in mean 636 changes are the same in the once-daily vs. twice-daily groups we shall consider the 637 results to be consistent with each other.

638

639 Secondary endpoints to be assessed in a descriptive manner include the following:

- 640 1. Coefficient of variation of TIR for each treatment within each group

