725 • Glucose meter and 100 test strips, to perform self-monitoring of blood glucose,
726 one box dispensed per patient. Source: Diabetes Care Center. Manufacturer:
727 Accucheck Aviva Plus
728

729 **8.2 Packaging and Labelling of Study Medication(s)**

730 • IDS will package the glargine and placebo as pre-filled syringed from vials 731
731 identically. IDS will then label the syringes with dose, dosing instructions, and 2
732 patient identifiers based on study drug request order entered by research staff, 733
733 after being notified about treatment assignment by IDS.
734 • IDeg will be dispensed in the original manufacturer's packaging, and IDS will 735
735 label IDeg with dose, dosing instructions, and 2 patient identifiers.
736 • Dexcom G6 Mobile CGM System will be distributed to patients in its original 737
737 manufacturer packaging.

738
739 Labelling of all medications and device will be in accordance with local law and study
740 requirements.
741

742 8.3 Storage and Drug Accountability of Study Medication(s)

743 All investigational and/or trial products received will be accounted for by the IDS. 744 Accountability logs are maintained for each product and dispensing is logged out as 745 individual line items. Other than syringes and needles, subjects will return used, partly 746 used, and unused products, and these will be documented on the accountability logs and 747 may be retained for reconciliation.

748

749 All products will be stored at the designated temperature (e.g. refrigerated or room 750 temperature) with temperature monitoring by the institutional system, TempTrak. This is 751 a continuous monitoring system with temperature time points taken every 15 minutes. 752 Temperature graphs are accessible via a web-based system. TempTrak sensors are 753 calibrated on a yearly basis. A second overlay is the use of Min/Max thermometers with 754 manual recording of temperature daily on Mon - Fri. All Min/Max thermometers have a 755 calibration certificate and are replaced prior to the expiration date.

756

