APPENDIX A: Sample Subject Daily Insulin Logbook, version-1.0

1106

Trial ID: U1111-1214-3257

1107

1108

Subject No. XX Subject Initials: ABC Subject DOB: MMDDYY

1109

1110

Date: MMDDYY Study Day: #

Time point	Time (hh:mm)	BG value (mg/dL)	Carbohydrates consumed (grams)	Bolus insulin dose NUTRITIONAL (units)	Bolus insulin dose CORRECTION (units)	Basal insulin dose (units)
Before breakfast						
Before lunch						
Before dinner						
At bedtime						
*Extra time point #1						
*Extra time point #2						
*Extra time point #3						

1111

* To be used only if needed. NOTE: please use these fields to enter any snacks consumed as well.

1112

1113

1114

Did you exercise today? [] yes or [] no

1115

1116

If yes, then please specify when and how long: from _____ to _____ (hh:mm)

1117

1118

1119

1120

1121

1122

1123

1124

1125

1126

1127

1128

1129

1130
1131 **APPENDIX B: Sample Subject Hypoglycemia Episode Form, version 1.0**
1132 (see Section 3.12 for details on directions to fill out this form)
1133
1134 Trial ID: U1111-1214-3257
1135 Subject No. XX Subject Initials: ABC Subject DOB: MMDDYY
1136
1137 Date: MMDDYY Study Day: #
1138
1139 1. When did the low BG start? _____(hh:mm)
1140 2. What was the lowest BG value during the episode? _____(mg/dL)
1141 3. Did you experience any of the following symptoms with this low BG?
1142 [] No or [] Yes (check all that apply)
1143 [] Sweating
1144 [] Trembling
1145 [] Feeling hungry
1146 [] Rapid or irregular heartbeat
1147 [] Feeling confused
1148 [] Feeling drowsy
1149 [] Speech difficulty
1150 [] Visual disturbances
1151 [] Odd behavior
1152 [] Impaired balance
1153 [] Reduced coordination of movements
1154 [] Headache
1155 [] Feeling discomfort or unease
1156 [] Seizure
1157 [] Loss of consciousness
1158 [] Other
1159 4. Were you able to manage it by yourself? [] yes or [] no. If no, please fill out Q9-
1160 12 as well. If yes, please skip Q9-12.
1161 5. How did you treat the low BG? _____
1162 6. When did the low BG resolve? _____(hh:mm)
1163 7. Did this episode happen in relation to physical activity? [] Yes or [] No
1164 If yes, then what were you doing? _____
1165 8. Were you asleep when the low blood glucose happened? [] Yes or [] No
1166 9. Who assisted in treatment of the episode? _____
1167 10. Where was the treatment administered? _____
1168 11. What treatment was provided to treat the episode? _____
1169 12. Were your symptoms alleviated by this treatment? [] Yes or [] No
1170
1171
1172
1173

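### The compliance definition does not name the blinded bridging/placebo syringe and is ambiguous by arm; delivery of the syringe is weakly documented, and departures from the correction-insulin restriction are logged but not classified

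*Combined protocol and SAP*

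**What the plan says.** Section 3.2 defines the contrast. On the transition night every patient takes the first IDeg dose and "a second injection from a pre-filled syringe of a pre-specified dose of insulin glargine or" matched saline. Patients and research staff are blinded.

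Section 3.13 requires three things in the 48 hours before and after the first IDeg dose: "No missed doses of basal insulin", "No missed doses of nutritional insulin with meals" and "Wearing the study CGM for >19 hours a day". It mentions neither the second syringe nor correction insulin.

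Section 12 has investigators judge "compliance with study drug based on" the patient's log and CGM wear. It says that patients who fail 3.13 are left out of all analyses and, in the same paragraph, that all randomized participants are included.

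The sample log in Appendix A has one column headed "Basal insulin dose (units" and one bedtime row. Correction boluses have their own column.

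The sentence on returns in section 8.3 begins "Other than syringes and needles, subjects will return used, partly" and goes on to cover partly used and unused products. Later the same section tells patients to return study drug whether used or not.

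Section 3.10.2.1 accepts that patients may not want to leave glucose between 180 and 250 "without correction, we feel this is a necessary part of our study protocol. The main reason" that follows is that corrections would dilute a difference in TIR. It sets the threshold at >250; inclusion criterion 13 sets it at ≥250.

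**The concern.** The trial tests one injection, so the record should show whether that injection was given. As written, a patient who skipped the syringe but took IDeg could complete the bedtime basal entry and look compliant.

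The first item of 3.13 also has a literal meaning that depends on arm, because saline is not insulin. With section 12 removing non-compliers, an item whose meaning depends on content is a poor basis for deciding who is analysed.

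The correction restriction raises a related problem. The protocol expects patients without the bridge to be tempted to correct and says this would shrink the measured difference. Yet a departure has no status under 3.13, while one missed meal bolus makes a patient non-compliant.

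This pilot is meant to guide a larger trial. A weak signal would be hard to interpret if delivery of the bridge and adherence to the restriction were not reported by arm.

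**Working it through.** **1. The plan's own figure.** Section 4 gives a difference of 15 points, common SD 15, 20 per arm and two-sided 0.05. SE = √(15²/20 + 15²/20) = 4.743. Noncentrality = 15/4.743 = 3.162 on 38 degrees of freedom. Power is 86.9% (88.5% by normal approximation). The stated 87% reproduces.

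**2. What 3.13 covers.**

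| Behaviour | Bridging arm | Direct arm |
|---|---|---|
| Syringe skipped, item 1 read literally | missed basal dose | not a missed basal dose |
| Syringe skipped, item 1 read as all study injections | missed | missed |
| Correction below the threshold | no status | no status |
| Meal bolus skipped | non-compliant | non-compliant |

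The wording does not settle which of the first two rows applies.

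**3. What would reveal a skipped syringe.** (a) The day-4 call (3.10.5), whose main purpose is to confirm that the transition was done correctly; this is self-report. (b) The log, where both 2100-hour injections fall in one basal column and bedtime row unless the patient uses an extra row. (c) Drug return, where 8.3 gives two instructions that disagree for a study drug supplied in a syringe.

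**4. What would reveal a correction departure.** The log holds time, glucose and correction units. Secondary endpoint 5 counts correction boluses but does not separate those below the threshold. For a day-3 transition the post-dose window ends at 2100 on day 5, and the only scheduled call inside it is on day 4.

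**5. Illustration: undetected missed bridging injections.** The documents give no rate, so a fraction m is assumed. Suppose these patients behave like direct conversion. The bridging mean becomes 15m, the difference 15(1−m), and the bridging variance 225 + m(1−m)·225.

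| m | Patients of 20 | Difference | Bridging SD | SE | Noncentrality | Power |
|---|---|---|---|---|---|---|
| 5% | 1 | 14.25 | 15.35 | 4.799 | 2.969 | 82.5% |
| 10% | 2 | 13.5 | 15.66 | 4.849 | 2.784 | 77.4% |
| 20% | 4 | 12.0 | 16.16 | 4.930 | 2.434 | 66.0% |

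With the SD held at 15, the 10% and 20% rows give 79.2% and 69.3%.

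**6. Illustration: corrections.** If corrections below the threshold shrank the difference to 13.5, 12 or 10.5 (assumed), power at SD 15 would be 79.2%, 69.3% or 57.8%.

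**7. Dropping patients instead.** Removing 2 or 4 bridging patients and leaving the difference at 15 gives 85.0% (18 vs 20) or 82.5% (16 vs 20). This looks better only as power arithmetic, since exclusion after randomization can itself bias the comparison.

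**The case against.** Much of the case on the other side stands.

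A reader might infer that the bridging injection lies outside the compliance definition. The documents do not support that. Section 3.2 treats study drug as the patient's basal insulin from the transition night, 8.1 lists saline among the study medications, and section 12 speaks of study drug generally. Item 1 can be read to cover the syringe.

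Nor do the documents show that exclusions will differ by arm. Staff who cannot see the content would probably treat a missed syringe alike in both arms. What remains is an ambiguity, harmless if read sensibly and easy to remove.

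The day-4 call is a real safeguard. An incorrect transition leads to a 3-day washout and a repeat, and a second error to discontinuation. The syringe is collected on the day it is used. The power losses therefore apply only to omissions that escape this call, and no document gives a rate.

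It would also be too strong to say that corrections are invisible or must pull the arms together. Glucose and corrections are logged, and the rule is a threshold, not a ban. Section 1 notes that over-correction can cause hypoglycemia, which could lower TIR in the direct arm and widen the difference.

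Finally, the log is a sample with three extra timed rows, and a returned empty syringe does not prove injection. Both points hold, but neither gives the second injection a record of its own.

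**Conclusion.** The point holds as a gap in wording and documentation. Section 3.13 should not leave the status of the blinded syringe to interpretation, and delivery of the only between-arm difference should not rest mainly on self-report and a shared log column. Departures from the correction restriction are recorded, but nothing in the plan classifies or summarises them as adherence, although the protocol ties them to the primary endpoint.

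The size cannot be fixed from the documents. Under assumed undetected omission of 5% to 20% in the bridging arm, with those patients responding as direct converters, power falls from 86.9% to between 82.5% and 66.0%. This shows sensitivity. It is not an estimate of the trial's power, and the stated 87% is not in error. The changes are worth making because they cost little.

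**What to change.** 1. **Section 3.13.** Keep the first item for all scheduled basal doses in the 48-hour windows and add: *including the blinded second syringe on the transition night, judged identically in both arms without reference to content.* Replacing the item with a transition-night rule would lose the check on the other basal doses.
2. **Appendix A.** Give the syringe its own line with time and units.
3. **Section 8.3.** Reconcile the two return statements so that the pre-filled study syringe comes back, used or unused, in a sharps container at Visit 3. This detects unused syringes; it does not prove injection.
4. **Correction rule.** Reconcile ≥250 (inclusion criterion 13) with >250 (section 3.10.2.1), and tabulate by arm the corrections logged below the reconciled threshold.
5. **Section 12.** Report syringe delivery and correction-rule departures as adherence alongside the primary result, not as new reasons to exclude randomized patients. Reconcile the two statements on who is analysed accordingly. One way is to analyse all randomized patients as the primary set and use 3.13 for a supportive analysis. Without this step, change 1 would widen post-randomization exclusion.

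The cost is protocol wording, a log reprint, a sharps container per patient and slight extra patient burden. The data for the correction table are already collected.
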